8.6. Data management

The completed CRFs will be sent by mail from the center to the CRO. Data will be entered at the CRO into an SAS-based database. All entries will be recorded in an audit trail file.

8.7. Data analysis

Absolute and relative adjusted frequencies are determined for categorical data. Numerical data are expressed using the sample statistics mean and standard deviation, as well as minimum, 1% percentile, 5% percentile, lower quartile, median, upper quartile, 95% percentile, 99% percentile and maximum.

The primary end point “proportion of patients attaining the desired treatment goal” will be analyzed using a logistic regression for the subgroups “RA patients with ETN+MTX” and “RA patients with ETN monotherapy”.

A detailed description of the statistical analysis of the data collected will be included in the SAP which will be dated, stored, and maintained by the sponsor. The SAP may modify the analyses described here. Every substantial amendment to the definition and analysis of the primary end point would take place in the form of a protocol amendment.

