8. STUDY METHODS

8.1. Study design

8.1.1. Design and study procedures

This study is a prospective, multicenter, non-interventional study to evaluate the efficacy of etanercept in patients with RA, PsA, axSpA or PsO.

Efficacy data will be documented within a period of 12 months and health outcomes every quarter in the course of routine treatment. An overview of the documentation to be performed can be found in Table 1 below.

Table 1: Overview of study procedures					
	Visit 1 Week 0	Visit 2 Week 12	Visit 3 Week 24	Visit 4 Week 36	Visit 5 Week 52
Medical history	X				
Inflammation in MRI (axSpA)	X				
Radiological Sacroiliitis (axSpA)	X				
Participation in the “Together” program	X				
Inclusion/exclusion criteria	X				
Treatment/medications					
Prior treatment	X				
Treatment with Enbrel	X	X	X	X	X
Concomitant treatment		X	X	X	X
Safety parameters					
Physical examination	X				
Laboratory	X	X	X	X	X
AE documentation		X	X	X	X
Efficacy					
Examination of joints	X	X	X	X	X
PASI (PsO)	X	X	X	X	X
Morning stiffness (RA, axSpA, PsA)	X	X	X	X	X
Patient and physician global assessment	X	X	X	X	X
Pain	X	X	X	X	X
Fatigue	X	X	X	X	X
Occiput-to-wall distance (axSpA)	X	X	X	X	X
Dactylitis (PsA)	X	X	X	X	X
Nail involvement (PsO, PsA)	X	X	X	X	X
Enthesitis (PsA, axSpA)	X	X	X	X	X
Pruritus (PsO)	X	X	X	X	X
Health outcomes					
FFbH (RA, axSpA, PsA)	X	X	X	X	X
BASDAI (axSpA)	X	X	X	X	X

DLQI (PsO)	X	X	X	X	X
PHQ-2	X	X	X	X	X

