8.1.2. Primary study end points

- Patients with RA: Proportion of patients who attain the desired treatment goals (see Table 2) at the week 12 and week 24 time points under monotherapy or in combination with MTX and maintain these long-term over a period of 52 weeks.
- Other indications: Proportion of patients who attain the desired treatment goals according to guidelines (see Table 2) in each respective indication at the week 12 and week 24 time points.

8.1.3. Secondary end points at weeks 12, 24, 36, and 52

All patients:

- Proportion of patients who continue treatment with etanercept,
- Occurrence of adverse events,
- Remission,
- Patient global assessment,
- Fatigue,
- Pain (VAS),
- Physician global assessment,
- PHQ-2
- Comparison of the parameters “patient global assessment,” “fatigue,” “pain,” “physician global assessment,” and “PHQ-2 across all indications,
- Comparison of FFbH and morning stiffness among patients with RA, axSpA, and PsA,
- Discontinuation of treatment due to a lack of efficacy or adverse events,
- Nature of further treatment if treatment has been discontinued,

Additionally for RA patients:

- FFbH
- CDAI
- SDAI

Additionally for axSpA patients:

- BASDAI,
- FFbH
- Enthesitis
- Occiput-to-wall distance

Additionally for PsA patients:

- BSA

- Dactylitis
- Enthesitis
- FFbH

Additionally for PsO patients:

- PASI, median time to PASI75, body segment (head, trunk, upper and lower extremities) and component-related subscales (erythema, induration, flaking) over 24 weeks,
- DLQI,
- Pruritus
- BSA.

The following indication-related laboratory tests will be documented if they are available as part of a routine assessment:

- Erythrocyte sedimentation rate (ESR), C-reactive protein (CRP)

In addition, the following laboratory tests will be documented for patients with RA, PsA, and axSpA if they are available as part of a routine assessment:

- Rheumatoid factor (RF) and anti-CCP antibodies.
- HLA-B27 at Visit 1 (just axSpA).

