8.5. Calculation of case numbers

It is assumed that the RA patients included in this study who are receiving a combined treatment (ETN + MTX) will be similar to those patients included in the randomized, double-blind DOSERA study in terms of the proportion of patients continuing treatment beyond week 12 (i.e. adequate efficacy - defined based on the DAS28 and the patient and physician global assessment of disease progression - has been attained). In that study, 22 - 26 % of the patients on combined treatment had attained no adequate efficacy after 12 weeks and continued treatment with etanercept (open-label), while conversely, adequate efficacy from treatment had been attained for 74 - 78 % of the patients at week 12. The sample size for this non-interventional study was calculated with the primary focus on the indication of RA.

Assuming that 74% of the patients under treatment with ETN + MTX and 66% of the patients under ETN monotherapy exhibit adequate response to treatment after 12 weeks (odds ratio of 0.682), 1200 patients (with a 2:1 ratio, this equals 800 patients under combined treatment and 400 patients under monotherapy) will be sufficient to detect a significant difference in the primary end point “proportion of patients attaining the desired treatment goal” with a power of 80% using a two-sided test with a significance level of 5%.

A logistic regression quoting the odds ratio and the corresponding 95% confidence interval is the appropriate statistical methodology for the analysis of this binary variable. As a sensitivity analysis, a GEE (generalized estimating equation) analysis can also be performed as a repeat method to obtain the binary response variable.

Because the combination with MTX is not recommended for the indications axSpA, PsO, and PsA, the inclusion of 300 patients in each of these indications appears sufficient for analysis of efficacy and tolerability.

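### The RA comparison of ETN+MTX with ETN monotherapy is non-randomised, yet 8.5 and 8.7 name no confounder adjustment and no section says when MTX status is fixed

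*Combined protocol and SAP*

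**What the plan says.** Section 8.5 assumes 74% adequate response at week 12 on ETN+MTX and 66% on monotherapy (odds ratio 0.682). It states that 1200 RA patients, 800 and 400, "will be sufficient to detect a significant difference in the primary end point" with 80% power, two-sided 5%. On method it says "A logistic regression quoting the odds ratio and the corresponding 95% confidence interval is the appropriate statistical methodology", with an optional GEE as a sensitivity analysis. Section 8.7 repeats that the end point "will be analyzed using a logistic regression for the subgroups" of RA patients with and without MTX. Neither section lists a covariate, propensity score, weighting or stratification for this model. The word adjusted in 8.7 refers to descriptive frequencies.

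The RA primary end point in 8.1.2 is goal attainment "at the week 12 and week 24 time points under monotherapy or in combination with MTX", with no rule for when a patient is classified or how a change of regimen is handled. In Table 1 (8.1.1), "Concomitant treatment" is marked at weeks 12, 24, 36 and 52 but not at Visit 1. "Prior treatment" is marked at Visit 1 only, without mention of MTX.

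Sections 6.2 and 8.3 mention influencing factors in general terms and do not tie them to the MTX odds ratio. Section 8.9 concedes that selection bias is possible and names no analytic remedy. Sections 8.3 and 8.7 defer detail to a separate SAP, and 8.7 adds: "The SAP may modify the analyses described here".

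**The concern.** Physicians and patients choose whether MTX accompanies etanercept, so the two groups may differ at baseline in features that also predict response. A logistic model containing only the regimen attributes those differences to MTX, and a larger sample narrows the confidence interval without removing the bias.

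Timing is a second, conditional problem. The first scheduled concomitant-treatment record falls at week 12, the visit of the first primary assessment. If groups were read from that record, patients who had added MTX because they were doing poorly on monotherapy would count as combination patients. Grouping would then depend on the outcome.

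At stake is the validity of the odds ratio and confidence interval for the one comparison that the study is formally powered to make.

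**Working it through.** **1. The plan's own figure.** Inputs from 8.5: p1 = 0.66 (monotherapy), p2 = 0.74 (combination), k = 2, two-sided 5%, 80% power. Odds ratio = (0.66/0.34)/(0.74/0.26) = 0.682. With p̄ = (0.66 + 2 × 0.74)/3 = 0.7133 and d = 0.08:

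- n1 = [1.960·√(1.5·p̄(1−p̄)) + 0.842·√(p1(1−p1) + p2(1−p2)/2)]² / d² = 381.2, total 1143.7.
- With continuity correction, n1/4 × [1 + √(1 + 2(k+1)/(k·n1·d))]² = 399.8, total 1199.3.

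This matches 1200, so the arithmetic is sound. It is the size for an unadjusted contrast; it does not show what the fitted model will contain. Uncorrected power at 800/400 is 81.8%.

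**2. Confounding, no true MTX effect (all inputs assumed).** The documents give no imbalance, factor effect or switching rate. Take a 40% goal rate without an adverse binary factor. Each group's rate is (1−q)·0.40 + q·r, where q is the factor's prevalence and r is the rate with the factor. For a factor OR of 0.5, r = 0.25; prevalences of 30% and 50% then give 0.7 × 0.40 + 0.3 × 0.25 = 35.5% and 0.5 × 0.40 + 0.5 × 0.25 = 32.5%. ORs below are monotherapy versus combination; rejection is for the pooled z test at 800/400.

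| Factor OR | Prevalence, combination / monotherapy | Crude OR | Rejection at nominal 5% |
|---|---|---|---|
| 0.7 | 30% / 40% | 0.97 | 5.8% |
| 0.5 | 30% / 40% | 0.94 | 8.0% |
| 0.5 | 30% / 50% | 0.87 | 17.6% |
| 0.4 | 30% / 50% | 0.84 | 25.8% |

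None of these reaches 0.682. In 2000 simulated trials of the last row, unadjusted rejection was 25.1%; adjusting for the factor brought it to 4.8% (OR 1.000).

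**3. Confounding, planned effect true (assumed).** Rates without the factor are the plan's 74% and 66%; factor OR 0.5.

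| Prevalence, combination / monotherapy | Rates, combination / monotherapy | Crude OR | Power |
|---|---|---|---|
| 30% / 30% | 69.4% / 61.0% | 0.688 | 82.9% |
| 40% / 30% | 67.9% / 61.0% | 0.739 | 66.0% |
| 30% / 40% | 69.4% / 59.3% | 0.642 | 93.4% |

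The same factor masks or exaggerates the effect according to which group carries more of it. In 2000 simulated trials of the 40%/30% case, adjustment restored OR 0.681 and power 84.7%.

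**4. Groups read at week 12 (hypothetical).** Suppose 5% or 10% of monotherapy non-attainers add MTX before week 12, are counted as combination, and have the same week-12 result as they would have had without it.

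| True rates, monotherapy / combination | Share moved | Patients moved | OR | Rejection |
|---|---|---|---|---|
| 40% / 40% | 5% | 12 | 1.08 | 9.3% |
| 40% / 40% | 10% | 24 | 1.17 | 23.1% |
| 66% / 74% | 5% | 6.8 | 0.741 | 60.9% |
| 66% / 74% | 10% | 13.6 | 0.807 | 35.8% |

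For the third row: 264/393.2 = 67.1% versus 592/806.8 = 73.4%. Moves in the other direction are possible.

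**5. Power of an adjusted model at N = 1200.** Log OR = 0.3827; SE = √[1/(400·0.66·0.34) + 1/(800·0.74·0.26)] = 0.1328. Power = Φ(0.3827·√(1−R²)/0.1328 − 1.96), where R² is that between MTX use and the covariates (assumed): 82.2% at 0, 80.2% at 0.05, 78.0% at 0.10, 73.1% at 0.20 and 67.4% at 0.30. This ignores any gain from covariates that predict response.

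**The case against.** The strongest reply is that the protocol delegates this. Covariate lists and exposure definitions are ordinary SAP content, and naming a model family is not the same as planning an unadjusted model. That stands: a reader might infer that no adjustment is planned, but with the SAP not supplied the documents cannot show it. What remains is that the protocol leaves the item open. An SAP also cannot recover a baseline status that was never recorded, and 8.7 itself requires a protocol amendment for a substantial change to the primary analysis.

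Second, baseline MTX may well be collected. Medical history, prior treatment and etanercept treatment are all marked at Visit 1, Table 1 is only an overview, and the CRF is not among the documents. Section 8.5 also describes the included RA patients as being on combined treatment, which reads most naturally as regimen at inclusion. So a reader might infer that baseline MTX goes unrecorded, or that groups will be formed at week 12; no section says either. Step 4 shows only why the rule should be written down.

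Third, the MTX contrast sets N but is not among the questions listed in section 7, and 8.9 disclaims proof of efficacy in the classical sense. It would be wrong to conclude that the main aim is compromised: the proportions benefiting after week 12, and their comparison across indications, do not depend on this odds ratio. The disclaimer does not, however, correct a biased odds ratio in a comparison powered for significance.

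Finally, the illustrations can be made to point either way, and the mildest barely exceeds 5%. That is correct, which is why step 3 shows both directions.

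**Conclusion.** The point holds as a gap in specification with a real analytic consequence. The RA contrast is non-randomised, 8.5 and 8.7 name no confounder control, and the time at which MTX status is fixed is not stated. If the model were run with regimen alone, its odds ratio would be open to confounding; if groups were taken from the week-12 record, it would also be open to outcome-dependent classification.

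The documents do not allow the size or direction to be known. Under the assumed inputs, rejection with no true effect runs from 5.8% to 25.8% through confounding, and is 9.3% or 23.1% through week-12 grouping. Power for the planned effect runs from 35.8% to 93.4%. These figures show sensitivity and are not estimates for this study. They do not support a claim that the result will favour combination treatment, nor that N = 1200 is miscalculated. This is a worthwhile, inexpensive improvement to a comparison outside the study's main question.

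**What to change.** 1. **Table 1:** mark concomitant treatment, including MTX, at Visit 1. Alternatively, state that the Visit 1 prior-treatment entry records ongoing MTX with start and stop dates.
2. **Section 8.7, groups:** define them by MTX status at etanercept start, which precedes any response. Because 8.1.2 can be read as the regimen received, analyse MTX actually received during follow-up as a sensitivity analysis.
3. **Section 8.7, model:** make the primary RA logistic model adjusted for prespecified covariates scheduled at Visit 1, such as disease duration, prior treatment, FFbH, patient and physician global assessment, joint examination, and DAS28 where ESR or CRP is available. State how missing covariates are handled and report the unadjusted odds ratio as supportive.
4. **Section 8.5:** keep N = 1200 and note that the 80% power refers to the unadjusted contrast. Adjusted power is about 80% to 67% for an assumed R² of 0.05 to 0.30, before any gain from prognostic covariates.

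The cost is one Visit 1 entry or a clarifying sentence and a short change to 8.7, by protocol amendment if judged substantial. No extra enrolment is needed. Two drawbacks remain. Missing covariates need a method, since for ESR and CRP section 8.1.3 says "The following indication-related laboratory tests will be documented if they are available as part of a routine assessment". Confounding by unmeasured factors will also persist.

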8.8. Quality control

Plausibility checks for the data entered will be defined in a data validation plan (DVP). As far as possible, these checks will be performed with software support and in the event of deviations, queries will be sent by the CRO to the centers. The sending and return of queries

will be tracked and if necessary, data changes will be performed in the database. All of the changes performed will be recorded in an audit trail file.

Furthermore, there it is provisionally planned that 30 monitoring visits will be performed at randomly selected centers to ensure data quality and to verify the documented patient data.

8.9. Strengths and limitations of the study methodology used

An inherent disadvantage of a non-controlled observational study is the potential risk of selection bias. Furthermore, patients who have withdrawn prematurely from the study, whose missing observations are not usually replaced, may skew the time point results toward the end of the study. Also, no proof of efficacy is possible in the classical sense as the data from a randomized parallel group are not available as a control.

However, these limitations are balanced by advantages associated with the methodology. For example, the design of an observational study usually permits the inclusion of a substantially larger number of patients that would be usual in randomized, controlled studies. Furthermore, in randomized clinical studies, only strictly selected patient groups are studied, which limits the applicability of these studies in terms of the patients who are ultimately treated in routine clinical practice. In the case of RA, it was shown based on evaluation of the German biologicals registry RABBIT that only 21 - 33% of the registry patients treated in routine clinical practice with TNF blockers would also have been eligible for participation in the pivotal randomized, controlled studies [14]. The patient groups selected from the clinical RA studies this reflect are only a small proportion of the patients who are routinely treated with biologicals in the postmarketing phase. As such, non-interventional observational studies, despite the limitations mentioned above, are capable of providing valuable supplemental information on the effects of a medication in everyday clinical practice.

8.10. Other aspects

Not applicable.

9. PROTECTION OF STUDY PARTICIPANTS

9.1. Patient information and informed consent form

All parties guarantee the protection of the patient's personal data and will not include the name of the patient in any forms from Pfizer, reports, publications or other disclosures unless required by law. In the event that data is forwarded, Pfizer will maintain high standards of confidentiality and the protection of the patients' personal data.

The informed consent form used in this study and all changes made in the course of the study must be approved in advance by Pfizer and submitted to the IRB/IEC for review before use.

The treating physician must guarantee that every study patient or her/his legal representative is informed fully of the characteristics and goals of the study and the potential risks associated with participation. The treating physician or a person assigned by her/him shall obtain a written informed consent form from every patient or patient's legal representative before study-specific activity is performed. The treating physician shall keep the original of every informed consent form signed by the patient.

9.2. Ending the participation of a patient

The patient can withdraw her/his consent to participate in the non-interventional study at any time or the treating physician may decide to end the participation of the patient on grounds of safety, problems with compliance, or for administrative reasons. In any case, the patient's clinical status should be documented if possible. The physician should ask the patient about the reasons for her/his decision and continue to track all unresolved adverse events.

If the patient withdraws her/his consent for further data collection, data will no longer be recorded from her/him as part of the non-interventional study.

9.3 Institutional Review Board (IRB)/Independent Ethics Committee (IEC)

The observational protocol and the patient information and informed consent form will be submitted to the competent ethics committee for review before patients are included.

9.4 Ethical study conduct

This study is a multicenter, prospective, non-interventional study in accordance with section 4, number (23), clause 3 of the AMG. Furthermore, the vfa recommendations for the improvement of quality and transparency in non-interventional studies apply, as do the guidelines of the "*Good Pharmacoepidemiology Practices*" (GPP), issued by the "International Society for Pharmacoepidemiology" (ISPE), the guidelines of the "International Society for Pharmacoeconomics and Outcomes Research" (ISPOR), and the guidelines of the "Pharmaceutical Research and Manufacturers of America" (PhRMA).

The patient shall provide her/his written informed consent form for the study, which will have been submitted to the Institutional Review Board (IRB)/Independent Ethics Committee (IEC) for review beforehand.

Based on the the vfa recommendations for the improvement of quality and transparency in non-interventional studies and in order to satisfy the requirement for publication of notice of NISs, this non-interventional study will be registered in a publicly accessible registry.

10. MANAGEMENT AND REPORTS FROM ADVERSE EVENTS/ADVERSE DRUG REACTIONS

10.1. Summary of product characteristics

Etanercept shall be used in accordance with the summary of product characteristics. The specified contraindications, warnings and precautions for use, undesirable effects, interactions, and information on posology and method of administration must be followed. All drug safety-relevant cases reported by the participating physician to the CRO contracted by Pfizer, Winicker Norimed, in the course of this non-interventional study will be evaluated based on the summary of product characteristics.

10.2. Requirements

The table below summarizes the requirements for the recording of safety-relevant events on the reporting form for adverse event monitoring (AEM) in non-interventional studies to Winicker Norimed. These requirements are described for three types of events: (1) serious adverse events (SAEs); (2) non-serious adverse events (if applicable) and (3) scenarios under which drug exposure occurs, including exposure during pregnancy, exposure during lactation, medication errors, overdose, misuse, extravasation, and job-related exposure. These events are defined in the section “Definitions of safety-relevant events”.

safety-relevant event	Notation in the case report form	Reporting on the NIS-AE reporting form to Winicker Norimed within 24 hours after discovery
SAE	All	All
Non-serious AE	all	all
Scenarios under which drug exposure occurs, including exposure during pregnancy, exposure during lactation, medication errors, overdose, misuse, extravasation, and job-related exposure.	All	All (regardless of whether they are associated with an AE)

For each adverse event (AE) the physician must track and collect information suitable for determining the outcome of the adverse event and for assessing whether it meets the classification criteria for an SAE (see the section “Serious adverse events” which follows). Safety-relevant events from the above table must be reported by the physician to Winicker Normied within 24 hours after s/he becomes aware of the event, **regardless of whether s/he sees any causal relationship with the medication being studied**. Especially when the serious

adverse event is fatal or life-threatening, the report to Winicker Normied must be made immediately, regardless of the scope of information available about the event.

These deadlines also apply for additional new information (follow-up) regarding reports of safety relevant events already submitted.

In the rare case that the physician is not immediately aware of the occurrence of a safety-relevant event, the physician must report the event within 24 hours after s/he becomes aware of it and must document the time at which s/he discovered the adverse event.

For safety-relevant events categorized as serious or listed in the right-hand column of the above table, which must be reported to Winicker Normied within 24 hours after they are discovered, the physician is obligated to track information and report it to Winicker Normied within the 24-hour deadline. Furthermore, a physician may be asked by Winicker Normied to expedite the collection of certain additional information. Such information may go beyond the scope and detail of the information about adverse events recorded in the case report form. Generally, this will involve the description of the adverse event in sufficient detail to permit a comprehensive medical evaluation of the case and independent determination of the possible causality. Also, all additional relevant information about the event, e.g. concomitant medications and illnesses, must be provided.

If a patient dies, a summary of any available autopsy findings must be submitted to Winicker Normied as soon as possible.

